11.3 Interim Analysis

A formal interim analysis with respect to the primary endpoint will be carried out after approximately 50% of patients completed the 28-Day follow-up or terminated the study early. The purpose of this interim analysis is to detect potential harm early. After the results become available, the DSMC will make recommendations to the Steering Committee concerning safety concerns and the appropriateness of continuing the study following Stopping Guidelines in section 11.7 of this protocol.

11.4 Statistical Inference

P-value-based claims about the primary efficacy outcome will be based on $p < 0.05$.

11.5 Planned Subgroup Analyses

Planned subgroup analyses for the primary endpoint include the following:

- Patient < 50 years of age vs. patients \geq 50 years of age
- Males vs. females
- Baseline DM vs. no DM
- Baseline CVD vs. no CVD
- Baseline HF vs. no HF
- Baseline HTN vs. no HTN
- On dexamethasone vs. not on dexamethasone
- On remdesivir vs. not on remdesivir
- On baricitinib plus remdesivir vs. not on baricitinib plus remdesivir
- On convalescent plasma vs. not on convalescent plasma
- On any of these: dexamethasone, remdesivir, baricitinib plus remdesivir, convalescent plasma vs. not on any of these
- Treated with monoclonal antibody infusion before hospital admission versus not treated with monoclonal antibody infusion before hospital admission

These potential subgroup effects will be explored using a treatment-interaction test (test for homogeneity).

11.6 Missing Values

All attempts will be made to minimize missing follow-up data. Data that are collected only at baseline will not be imputed.

For missing primary and secondary outcome data a multiple imputation algorithm will be applied, using the technique of White et al. (White, Royston, and Wood 2011). This assumes the outcome is missing at random after taking into account the association of the outcome with baseline characteristics in patients with complete data. 25 consequent complete data sets will be generated and the combined treatment effect estimate, 95% confidence interval and P-value will be obtained using Rubin's rule.

For the primary outcome an additional tipping point analysis will be conducted should the above analysis be statistically significant at the 5% level, as follows.

For patients with missing outcome data a two-way display of all possible numbers with the primary outcome in each treatment group will have the consequent P-values calculated. Those with P above 0.05 will indicate the tipping points for which the positive primary analysis would be contradicted.

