6 STUDY DESIGN

6.1 Summary of Study Design

Multi-center, double-blind, randomized, placebo-controlled, parallel group design. 1:1 randomization.

Screening (Assessment Day 0-1): Patients hospitalized for COVID-19 will be screened. If patient consent can be obtained, baseline assessments will be carried out: Physical examination (including vital signs), ECG (including QTc interval assessment), echocardiography, chest X-ray, local laboratory assessments, including CBC, AST/ALT, alkaline phosphatase, bilirubin, creatinine/eGFR, INR, serum pregnancy test (in women with child-bearing potential only), glucose, total cholesterol, lymphocyte count and LDH. Frozen samples will be retained for central analysis of CardiolRx™ levels, hs-troponin, NT-proBNP, D-dimer as well as inflammatory markers (hs-CRP, ferritin, TNF-alpha, IL-1 beta IL-6, IL-10). A C-SSRS will also be completed.

If all eligibility criteria are met, the patient will be randomized to either CardiolRx™ or placebo.

Study treatment will be initiated in the evening of Day 1, after all baseline assessments have been completed and the patient is randomized. Study medication must be taken with food. The maximum dosing period of patients will be 28 days.

Oral administration is as follows:

Study Day	a.m. dose [mg/kg of body weight] CardiolRx™ or placebo	p.m. dose [mg/kg of body weight] CardiolRx™ or placebo
1	N/A	2.5
2	2.5	2.5
3	2.5	5
4	5	5
5	5	7.5
6 - 28	7.5	7.5

If the next higher dose is not tolerated, the dose will be reduced to the previous tolerated dose. The highest tolerated dose will be administered until Day 28.

At each study visit, drug accountability will be done. New bottles of study medication will be dispensed at each study visit (Days 3, 5, 7, 14 and 21).

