6.7.3 Withdrawal of Consent

Patients may decide to fully or partially withdraw their consent to participate in the study. At that point, it should be established, whether the withdrawal is related to study treatment, further assessments, or any further involvement in the study. If the withdrawal is primarily related to study treatment or specific assessments, patients should be encouraged to continue follow-up and to attend all other subsequent study assessments. Reports of AEs and SAEs should be collected until completion of the study for all withdrawals, unless the patient objects to such follow-up.

Patients who withdraw their consent to participate in the study, whether related to study treatment or not, will not be replaced. All data available will be included in the statistical analysis.

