9.2.8 Ordinal Outcome Scale

The scores for the Ordinal Outcome Scale will be collected at each visit:

- 1) not hospitalized and no limitations of activities;
- 2) not hospitalized, with limitation of activities, home oxygen requirement, or both;
- 3) hospitalized, not requiring supplemental oxygen and no longer requiring ongoing medical care
- 4) hospitalized, not requiring supplemental oxygen but requiring ongoing medical care
- 5) hospitalized, requiring any supplemental oxygen;
- 6) hospitalized, requiring noninvasive ventilation or use of high-flow oxygen devices;
- 7) hospitalized, receiving invasive mechanical ventilation or extracorporeal membrane oxygenation (ECMO);
- 8) MI or stroke diagnosed since randomization
- 9) death.

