10 CRITERIA FOR EVALUATION OF STUDY RESULTS

10.1 Criteria for Evaluation of Efficacy

10.1.1 Primary efficacy outcome

The primary efficacy outcome is the percentage of patients who experience one of the following events during the first 28 days:

- All-cause mortality
- Requirement for ICU admission and/or ventilatory support due to COVID-19
- CV complications*:
 - HF or
 - AMI or
 - myocarditis or
 - new sustained or symptomatic arrhythmia or
 - stroke

*see definitions in Appendix 17.8

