11 STATISTICAL METHODS

11.1 Sample Size Estimation

Assuming that 19% of patients qualifying for the study in the placebo group would develop one or more primary outcomes, a treatment effect of lowering the event rate by 50% (i.e., only 9.5% of patients treated with CardiolRx™ would experience a primary outcome event, a two-sided alpha of 0.05 and 80% power, 211 patients per group (422 in total) would be required.

Consideration will be given to adjust the sample size just before the interim analysis, should the observed event rate differ from the assumption above. Consideration will also be given to upgrading the Ordinal Outcome Scale first secondary endpoint to be the primary endpoint should the event rate of the current primary endpoint be significantly lower than the above assumption. This would be carried out in a blinded fashion. If the overall primary event rate is lower than $(19 + 9.5)/2 = 14.25\%$, the sample size will be increased to preserve 80% power to detect a 50% relative reduction with a two-sided alpha of 0.05.

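### Protocol 11.6 imputes a missing 28-day primary outcome without using the event-free time already observed, so it overstates risk and lets unequal loss shift the treatment effect

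*Protocol*

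**What the plan says.** The primary outcome (Protocol 10.1.1) is binary: the "percentage of patients who experience one of the following events during the first 28 days". For missing primary and secondary outcomes, Protocol 11.6 plans chained-equation multiple imputation with 25 data sets pooled by Rubin's rule, assuming the outcome is "missing at random after taking into account the association of the outcome with baseline characteristics in patients with complete data". It names no follow-up information and does not say whether treatment arm is in the model. A tipping-point display for the primary outcome follows only if the imputed analysis is significant at 5%.

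Other sections bear on the point:

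- Protocol 9.2.8 supplies post-baseline data: "The scores for the Ordinal Outcome Scale will be collected at each visit".
- Protocol 6.7.3 says of patients who withdraw consent: "All data available will be included in the statistical analysis".
- Protocol 6.7.1 keeps patients who stop study drug in follow-up unless they withdraw consent.
- Protocol 11.2.1 adds a Cox model for time to first event, labelled exploratory, and Kaplan-Meier plots by arm.
- SAP 6.6.5 applies no imputation except for dates. SAP 9.1.1 performs no primary analysis and only lists subjects with a composite event. Both follow from early termination.

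**The concern.** Once a patient has any component event, the composite is known, whatever happens to follow-up afterwards. Loss to follow-up therefore leaves the outcome missing only in patients who were event-free at last contact. Such a patient faces only the risk of the days not yet observed.

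A model learned from complete cases on baseline characteristics assigns the risk of the whole 28 days instead. It assigns slightly more than that, because a patient whose event came before the time of loss counts as complete, while an event-free patient lost at the same time does not. Complete cases are thus enriched for events.

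The excess in an arm grows with the share lost in that arm. If loss differs between arms, the errors do not cancel, and the difference in proportions, on which the primary claim rests, moves against the arm with more loss.

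**Working it through.** **Inputs from the documents.** Protocol 11.1: "Assuming that 19% of patients qualifying for the study in the placebo group would develop one or more primary outcomes" and "only 9.5% of patients treated with CardiolRx™ would experience a primary outcome event", with "a two-sided alpha of 0.05 and 80% power, 211 patients per group (422 in total) would be required". The pooled two-proportion formula without continuity correction gives 211.4, or 212 per group rounded up. Power at 211 per group is 79.9%. The plan's figure reproduces.

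**Assumed inputs.** *f* is the share of 28-day events that occur before the time of loss (70% and 90%). *l* is the share then lost among patients still event-free (5-15%). Loss is independent of event time. The documents give none of these.

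**Formulas, per arm with 28-day risk *p*.**
- Lost: *L* = *l*(1 − *pf*)
- Observed events: *O* = *pf* + (1 − *l*)*p*(1 − *f*)
- True residual risk of a lost patient: *p*(1 − *f*)/(1 − *pf*)
- Risk imputed with arm in the model: *O*/(1 − *L*), which is also the arm's estimated total
- Risk imputed with arm omitted: *R* = (sum of *O*)/(sum of 1 − *L*) over both arms, giving an arm total of *O* + *L* × *R*

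**Residual risk.** At *f* = 0.9: placebo 0.019/0.829 = 2.3%, active 0.0095/0.9145 = 1.0%. At *f* = 0.7: 6.6% and 3.1%.

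**Worked case: *f* = 0.9, loss 5% placebo and 15% active.**
- Placebo: *L* = 0.05 × 0.829 = 0.04145; *O* = 0.171 + 0.95 × 0.019 = 0.18905; total 0.18905/0.95855 = 19.72%.
- Active: *L* = 0.15 × 0.9145 = 0.13718; *O* = 0.0855 + 0.85 × 0.0095 = 0.09358; total 0.09358/0.86283 = 10.85%.
- Difference 8.9 points against a true 9.5.
- No true effect (19% in both arms): the active arm becomes 0.18715/0.87565 = 21.37%, against 19.72% on placebo, a spurious harm of 1.7 points.
- Arm omitted: *R* = 0.28263/1.82138 = 15.5%; totals 19.55% and 11.49%; difference 8.1 points.

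**Results over *f* = 0.7 to 0.9.** True difference is 9.5 points under the design effect and 0 under the null. The first two results have arm in the model.

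| Loss, placebo / active | Design effect | Null (minus = harm) | Design effect, arm omitted |
|---|---|---|---|
| 10% / 10% | 10.0-10.2 | 0 | 9.1-9.3 |
| 5% / 10% | 9.4 | −0.6 to −0.8 | 8.7-8.8 |
| 5% / 15% | 8.9-9.0 | −1.3 to −1.7 | 8.1-8.2 |
| 15% / 5% | 11.0-11.5 | +1.3 to +1.7 | 10.0-10.5 |

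With equal loss and arm in the model both rates rise in near proportion, so the risk ratio stays at 0.50 while each rate is overstated (at 10% loss, placebo 20.2-20.5% and active 10.2-10.4%).

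**Check with different timing.** Loss uniform over 28 days, with events at constant hazard or early (exponential, mean 5 days), arm in the model. At 10% loss the imputed placebo risk is 19.9-20.4% against a true residual of 3.9-10.2%. At 5%/15% loss the expected difference is 8.9-9.2 points and the null shift 1.0-1.5 points. At 5%/10% they are 9.4 and 0.5-0.7.

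In simulation (211 per arm, 25 imputations, Rubin's rule, Wald test on the difference, 4000 runs), type I error at 5%/15% was 5.7-6.5%, and at 5%/20% it was 6.3-8.6%, against 4.5-4.8% with no loss. Power at 5%/20% was 63-69% against about 82% with no loss; part of that fall is lost information, not bias.

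**Check of the remedy.** Imputing the residual risk gives *pf* + (1 − *l*)*p*(1 − *f*) + *l*(1 − *pf*) × *p*(1 − *f*)/(1 − *pf*) = *p*. Each arm returns exactly to its true risk for any *l*, provided loss is independent of event time.

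**The case against.** The strongest objection is that this analysis will not be run. The SAP removes the imputation and the primary comparison, so a reader who infers that the trial's reported primary result is biased goes beyond the documents: no primary treatment effect will be estimated. This stands and limits the point to Protocol 11.6 or a reinstated analysis.

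Second, a reader might infer that treatment arm is left out of the model. Section 11.6 states an assumption and does not list predictors, so the 8.1-8.2 point figure rests on silence. This also stands. The main figures therefore assume that arm is included, and the bias remains.

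Third, the size depends on imbalance. With arm in the model, 5% against 10% loss moves the design effect by about 0.1 point. Patients lost in the first days do carry nearly the full risk, and follow-up after stopping drug (6.7.1) and after partial withdrawal (6.7.3) should limit loss. All of this is fair.

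Fourth, safeguards exist. The Cox and Kaplan-Meier analyses use event-free time, but they do not carry the primary claim. It would be too strong to say that the tipping-point display is useless: a spurious benefit that reaches significance triggers it, and it covers all possible event counts in each arm. The gap is on the other side. A real benefit masked by heavier active-arm loss, or a spurious harm short of significance, never triggers it.

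Finally, outcomes could also be missing because records are too incomplete to adjudicate (12.6). The mechanism here covers loss to follow-up only.

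**Conclusion.** The concern holds for Protocol 11.6 as written, within limits. The stated assumption discards observed event-free time, gives patients lost event-free at least the full 28-day risk, overstates event rates, and shifts the comparison against the arm with more loss.

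The shift is small for a 5-point imbalance in loss. It becomes material at 10 points or more: roughly half a point off a true 9.5-point effect, and a spurious difference of 1.3-1.7 points under the null. These sizes rest on assumed loss rates, 70-90% of events preceding loss, loss independent of event time, and arm in the model. The direction under unequal loss does not depend on the exact values. Nothing here bears on results reported under the current SAP.

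**What to change.** In Protocol 11.6, and in the SAP if the analysis is reinstated, impute only the unobserved remainder of the 28 days, for example through visit-interval hazards. Condition on treatment arm, baseline characteristics, time of last event-free contact and last Ordinal Outcome Scale score. Alternatively, compare Kaplan-Meier Day 28 risks between arms. Name the variables in the text, and run the tipping-point display whatever the primary p-value.

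The scale is already scheduled at every visit, so no new data are needed. The cost is a change of wording and some extra programming, with no change to the sample size.

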11.7 Stopping Guidelines

The DSMC will evaluate the results of the interim analysis after approximately 50% of patients have completed the 28-Day assessment (or terminated the study early) with

PROPRIETARY AND CONFIDENTIAL

respect to prospectively defined criteria and make recommendations concerning safety concerns and the appropriateness of continuing the study.

Early stopping criteria:

The DSMC will recommend stopping the trial for safety reasons if there is a statistically significant imbalance of deaths in the active vs. the placebo group at a $p<0.05$ level, as determined by a two-sided Fisher's Exact test. In addition, the DSMC has the right to recommend stopping the trial early for evidence of harm that was not pre-defined by a formal stopping rule.

It is unlikely for the trial to stop early for overwhelming efficacy ($p<0.001$). Therefore, no stopping rule for superiority will be applied in order to collect sufficient data on secondary endpoints and evaluation of safety.

12.2 Project Management Team

The Sponsor will select qualified team members for a Project Management Team, responsible for overall study management, including preparation of all study material and procedures, safety reporting, data quality assurance as well as for the maintenance of the trial master file. The Project Management Team will also be responsible for organization of meetings, site initiation and training, on-site monitoring and study close-out and will issue regular progress reports and newsletters to be sent to investigators and committees. The members of the Project Team are listed in Appendix 17.9. WWCT will support the Project Management Team and will carry out tasks as described in the contractual agreement between WWCL and the Sponsor.

12.3 Data Management Centre

A Data Management Centre will be established at WWCT. WWCT will be responsible for preparing the e-CRF and the database as well as the database management, in-house data monitoring, data handling, cleaning and statistical reporting.

12.4 Steering Committee

A Steering Committee will be appointed, which will include the Study Chair and a minimum of four other clinicians. The Steering Committee will be responsible for providing clinical and methodological guidance, including overall study design, execution, analysis, and publication of the main study results. The Steering Committee will oversee the management of the clinical trial sites and will also act as the Publication Committee.

While the study is ongoing, the Committee will approve any protocol amendment that may become necessary and is responsible for maintaining the scientific integrity of the study. Steering Committee meetings may include representatives from the Sponsor and from the Data Management Centre.

The Steering Committee will receive recommendations from the Data Safety and Monitoring Committee (DSMC) regarding the appropriateness of continuing the study. The final decision will rest with the Steering Committee.

12.5 Data Safety and Monitoring Committee (DSMC)

An independent DSMC will be established. The committee will consist of at least two clinicians and a statistician who are not otherwise associated with the study. The DSMC will review all SAEs after 50 patients have completed the 28-Day assessment (or terminated the study earlier) and on an ongoing basis by treatment code.

The DSMC will also conduct unblinded reviews of the QTc intervals measured in the first 100 patients and make recommendations to the Steering Committee concerning safety concerns and the appropriateness of continuing the study.

The DSMC will evaluate the results of the interim analysis after approximately 50% of patients have completed the 28-Day assessment (or terminated earlier) with respect to prospectively defined criteria for declaring harm and futility, as documented in section 11.7 of this study protocol and in the DSMC Charter.

In addition, the DSMC has the right to recommend stopping the trial early for evidence of harm that was not pre-defined by a formal stopping rule.

12.6 Adjudication Committee

This Committee consists of at least three clinicians who have been appointed by the Steering Committee. The members of the Adjudication Committee will classify all SAEs to pre-specified definitions, as described in the Event Classification Manual, based on medical records and other documents. In addition, all endpoints will be verified by the Adjudication Committee.

13 DATA COLLECTION AND MONITORING

13.1 Case Report Forms (CRFs)

Electronic data capture will be used for this trial, meaning that all study data will be entered in electronic case report forms (eCRF) at the investigational site. Data collection will be completed by authorized study site personnel designated by the Investigator. Appropriate training and security measures will be completed with the Investigator and all authorized study site personnel prior to the study being initiated and any data being entered into the system for any study patients.

The study data will be housed on a secure in-house server at WWCT throughout the duration of study, and up to 10 years after the study is complete. An encrypted CD of the tabulated study data will be stored at the WWCT for 25 years after completion of the study.

13.2 Data Collection and Cleaning

13.2.1 Data collection

Records for all patients from whom an Informed Consent is obtained will be stored on a secure eCRF that will be maintained at the Data Management Centre. All eCRF corrections are to be made by an investigator or other authorized study site personnel. The investigator/co-investigator must confirm by his/her electronic signature in a specific section of the eCRF that he/she has reviewed the data, and that the data is complete and accurate.

13.2.2 Data validation

Data validation procedures will be described in detail in the Data Management Plan.

13.3 Monitoring

13.3.1 Virtual monitoring

The Project Management Team is responsible for monitoring according to applicable local GCP standards and ICH guidelines to ensure the completeness, correctness, and consistency of the data and to assess whether the study is executed according to this protocol. Specific items to be checked are listed in the Investigator's Study File.

To verify that the CRFs are completed accurately and in accordance with source documents, source data verification will be performed. The CRFs and related source documents will be reviewed in detail by the on-site monitor during each visit. Checks for completeness and correctness of the data will be done by comparing CRF entries with information in the patients' local medical records.

13.3.2 Data Review and Cleaning

In-house data review and cleaning will be performed by WWCT. In case of missing, erroneous or incomplete data, further information will be requested by WWCT via electronic Data Clarification Forms (eDCFs). These are sent directly to the investigator and copied to the monitor in charge of the site.

13.3.3 Audit/Inspection

The Sponsor, WWCT and/or a competent authority may perform audits. The auditor/inspector must have access to all study and source documentation, facilities and equipment used in this study. The Steering Committee will supervise audit procedures and is entitled to initiate audits on its own.

14 INVESTIGATOR RESPONSIBILITIES AND OBLIGATIONS

14.1 Declaration of Helsinki

The study will be carried out in accordance with the provisions of the Declaration of Helsinki (last revised version, see Appendix 17.1) and with applicable local GCP standards.

